## **19.4 Secondary endpoint analysis**

In the Clinical Need Cohort, analysis will only be performed for the overall survival, response to next treatment for CLL and time to next treatment, and the toxicity and tolerability endpoints. Clinical Need Cohort outcomes will not be compared with randomised pathway. Unless stated otherwise all secondary endpoints will use the ITT population in the Randomised Pathway. All analyses will be conducted with a 2.5% significance level unless stated otherwise.

### **19.4.1 Overall Survival**

In the Randomisation Pathway, Cox regression analysis will be used to analyse overall survival accounting for the stratification factors (excluding centre), and Kaplan-Meier curves will be presented. Participants not known to have died at the time of the analysis will be censored at the last date they were known to be alive. The aim of this secondary endpoint will be to show the non-inferiority of the intermittent strategy in comparison to the continuous strategy. This will be assessed in both the ITT and PP populations and will need to show non-inferiority in both to conclude non-inferiority in this endpoint. This comparison is not powered.

There will be no formal comparison of OS in the Clinical Need Cohort with the OS survival in the randomisation pathway.

### **19.4.2 Toxicity and Tolerability**

Safety analyses will summarise the AR, SAE, SAR and SUSAR rates per participant, by treatment arm, overall and also in the Clinical Need Cohort. Suspected relationship to the protocol treatment will be presented along with other causality, outcome and event duration. ARs will be presented by CTCAE toxicity grade (V5). Individual AR/SAE line listings will be reported by treatment arm and MedDRA System Organ class (where applicable). Treatment related mortality rates will be presented by treatment received. This analysis will be over the safety population.

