# 14 PHARMACOVIGILANCE PROCEDURES

## 14.1 General definitions

The standard definitions are derived from the document 2011/C 172/01 ‘Detailed guidance on the collection, verification and presentation of adverse event/reaction reports arising from clinical trials on medicinal products for human use (“CT-3”)’ (based on the Clinical Trials Directive 2001/20/EC) and from the CIOMS Working Group VII definitions.

Term	Definition
Adverse Event (AE)	
Any untoward medical occurrence in a patient or clinical trial subject administered a medicinal product and which does not necessarily have a causal relationship with this treatment.
 
An adverse event can therefore be any unfavourable and unintended sign (including an abnormal laboratory finding, for example), symptom or disease temporally associated with the use of a medicinal product, whether or not considered related to the medicinal product.

Adverse Event of Special Interest (AESI)	
An adverse event of special interest (serious or non-serious) is one of scientific and medical concern specific to ibrutinib, for which ongoing monitoring and rapid communication by the investigator to the sponsor could be appropriate. Such an adverse event might require further investigation in order to characterise and understand it. Depending on the nature of the adverse event, rapid communication by the trial sponsor to other parties (e.g. regulators) might also be warranted.

Adverse Reaction (AR)	
All untoward and unintended responses to an IMP related to any dose administered.
 
This definition covers also medication errors and uses outside what is foreseen in the protocol, including misuse and abuse of the product.
 
This definition implies a reasonable possibility of a causal relationship between the event and the IMP. This means there are facts (evidence) or arguments to suggest a causal relationship.

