### 14.4.1 AEs and ARs

AEs may be spontaneously reported by the participant and/or in response to an open question from study personnel or revealed by observation, physical examination, or other diagnostic procedures, and should be reviewed at each cycle of protocol treatment. Any clinically relevant deterioration in laboratory assessments or other clinical finding is considered an AE, whether or not it is considered related to the IMP, if it meets the criteria of an AE or causes a change in the action taken.

When possible, signs and symptoms indicating a common underlying pathology should be noted as one comprehensive event.

All adverse events, both related and unrelated to CLL treatment will be collected on the relevant eCRF from trial registration until 60 days after the last dose of protocol treatment.

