#### **17.4.3 Toxicity and Tolerability**

Toxicity and tolerability will be reported based on the adverse events, as graded by CTCAE V5.0 and determined by routine clinical assessments at each centre. SAEs will be reported according to MedDRA System Organ Class.

For the Clinical Need Cohort this endpoint will be defined as above.

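### Toxicity is defined on all adverse events, but 19.4.2 counts and grades non-serious events only when they are attributed to ibrutinib, in an analysis set that omits pausing participants who never restart

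*Protocol*

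**What the plan says.** - **Endpoint (Protocol 17.4.3).** "Toxicity and tolerability will be reported based on the adverse events, as graded by CTCAE V5.0". Nothing here restricts the endpoint to related events.
- **Collection (14.4.1).** "All adverse events, both related and unrelated to CLL treatment will be collected", from registration to 60 days after the last dose.
- **Analysis (19.4.2).** "Safety analyses will summarise the AR, SAE, SAR and SUSAR rates per participant", by arm and for the Clinical Need Cohort. CTCAE grades are promised for ARs only, and line listings for ARs and SAEs. The analysis uses the safety population, which 19.1 limits to participants with at least one on-study dose.
- **Definitions (14.1).** An adverse event "does not necessarily have a causal relationship with this treatment". For an adverse reaction, "This definition implies a reasonable possibility of a causal relationship between the event and the IMP". An SAE is defined by its seriousness, whatever its cause.
- **Design (8.1).** The trial is open-label, and the intermittent arm stops ibrutinib as soon as it is randomised.

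**The concern.** The endpoint and its analysis do not cover the same events. A non-serious event of any grade enters 19.4.2 only after someone has linked it to ibrutinib. Section 6.3 names arthralgia, bruising, rash and hypertension among the long-term toxicities, and such events can be non-serious.

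The restriction does not act equally on the two arms. An event in a participant who is not taking ibrutinib is less likely to be called a reaction to it, and the assessor knows the participant's drug status. A lower AR rate under pausing could therefore come from less toxicity, from less attribution, or from both, and the planned tables could not separate them.

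This matters because 18.1 gives an expected reduction in toxicity as one of the reasons why the possible loss in PFS was accepted as clinically tolerable. The toxicity data will be read as the test of that expectation.

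**Working it through.** The plan gives no figure to reproduce, so the check is mainly textual.

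**1. Which events reach the analysis**

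| Type of event | In endpoint (17.4.3) | Collected (14.4.1, 14.4.4) | Summarised (19.4.2) |
|---|---|---|---|
| Serious, any cause | yes | yes | yes, as SAE |
| Serious, related | yes | yes | yes, as SAR or SUSAR |
| Non-serious, related | yes | yes | yes, as AR, with grade |
| Non-serious, not judged related | yes | yes | no |

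The last row is the gap. Since grades are presented for ARs only, no all-cause table by grade is planned either.

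**2. Can attribution alone produce a difference?** Assume the same all-cause AE rate r in both arms. Let f be the share of time on drug in the pausing arm, and let q and q_off be the probabilities that an event is attributed to ibrutinib on and off drug.

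- Continuous arm AR rate: r × q
- Pausing arm AR rate: r × [f × q + (1 − f) × q_off]
- Ratio, pausing to continuous: [f × q + (1 − f) × q_off] / q = 1 − (1 − f) × (1 − q_off/q)

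The rate r cancels. The ratio is below 1 whenever f < 1 and q_off < q, although the all-cause ratio is 1.00.

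None of f, q or q_off is in the protocol, so these values are assumed:

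| f | q_off = 0 (any q) | q = 0.3, q_off = 0.05 | q = 0.6, q_off = 0.05 |
|---|---|---|---|
| 0.2 | 0.20 | 0.33 | 0.27 |
| 0.4 | 0.40 | 0.50 | 0.45 |
| 0.6 | 0.60 | 0.67 | 0.63 |
| 0.8 | 0.80 | 0.83 | 0.82 |

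For example, f = 0.4, q = 0.3 and q_off = 0.05 give (0.12 + 0.03)/0.3 = 0.50. The table shows direction and sensitivity; it does not estimate the bias in this trial.

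**3. Who is analysed.** Continuous-arm participants enter the safety population with their first dose after randomisation. Pausing participants enter only when they restart. Read literally, 19.1 removes anyone whose first pause lasts until the analysis, so the pausing arm becomes a group selected on an outcome after randomisation. It also loses the participants with least drug exposure, which can work against pausing. This effect and the one in step 2 may pull in opposite directions.

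**4. Whether pauses are covered by collection.** Section 14.4.1 collects AEs from registration to 60 days after the last dose. Appendix 4 starts AE review at the first treatment dose, which for a pausing participant could mean the restart. Section 14.4.4 collects SAEs from registration to 30 days after the last dose. None says whether the last dose before a planned pause ends the window. Section 13.8.1 does schedule AE assessment every 3 months in both arms, which suggests that pauses are meant to be covered.

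**The case against.** The strongest reply is that 19.4.2 already includes SAE rates by arm, which are free of the attribution problem. The section is descriptive, with no test and no decision rule. QoL is analysed separately (19.4.4), the DMEC sees cumulative safety data by arm (20.3), and an unseen SAP may add AE tables. The point about SAEs stands in full: serious events are compared regardless of cause. The rest lowers the stakes but leaves the mismatch, because 19.4.2 states which events will be summarised and so makes a choice that the SAP would have to depart from.

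A reader might infer more than the text supports:

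- **That toxicity is analysed only through attributed reactions, so pausing must win.** The SAE rates rule out the first part. Some AR reduction would also be a true effect of less exposure, and the safety population may push the other way.
- **That the apparent reduction can be given as a percentage.** Every input to such a figure would be assumed.
- **That the 3 to 9 years on trial bias per-participant rates.** That range follows from entry date (8.1), and concurrent 1:1 randomisation should balance it between arms.
- **That unblinded investigators are documented as attributing every event.** Sections 14.4.4 and 14.6.1 say so for serious events, and 14.6.3 adds review by the Chief Investigator or a delegate. For non-serious ARs it is an inference, though a natural one in an open-label trial.

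**Conclusion.** The point holds in a limited form. Sections 17.4.3 and 19.4.2 disagree on which non-serious events make up the toxicity endpoint, and the version fixed for analysis depends on knowledge of drug status. The AR, SAR and SUSAR comparisons can favour pausing without any difference in all-cause events; the SAE comparison is not open to this. The conclusion on direction rests on one assumption, that events are less often attributed to ibrutinib during a pause than on drug. The size is unknown: the ratios of 0.20 to 0.83 only illustrate assumed inputs.

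Separately, the safety population as worded does not compare the arms as randomised, and its effect may run against pausing. The net direction across the planned safety tables is therefore not settled. The primary analysis is untouched. The change should be made because reduced toxicity is part of the case for the margin and the remedy is cheap.

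**What to change.** 1. In 19.4.2, make all-cause AEs (any grade, and grade 3 or higher) and SAEs the main between-arm summary, by allocated arm in all randomised participants.
2. Use the same calendar window from randomisation in both arms, and state that it includes planned pauses.
3. Align the AE and SAE collection windows in 14.4.1, 14.4.4 and Appendix 4 with that window, and say what the last dose means for a participant on a planned pause.
4. Keep ARs and SARs as supportive tables, split by on-drug and paused time, and add exposure-adjusted rates.

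The cost is extra tables, largely from data that 14.4.1 and 13.8.1 already call for, and one clarification of the collection windows. If sites have so far read the windows as closing during a pause, some paused-time events may be missing, so the clarification should come early.

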### **19.4.3 The Cost Effectiveness of the Intermittent Treatment Strategy**

An economic evaluation of continuous versus intermittent treatment will be conducted following the NICE reference case with the primary outcome being incremental cost per quality-adjusted life year (QALY) gained. The perspective will be that of the health care and personal social service provider. Utility values will be generated during the trial using the EQ-5D-5L (23) and EORTC-8D (24). Currently, NICE advise the use of a published (EQ-5D-5L to EQ-5D-3L) mapping algorithm to generate the utility index from the EQ-5D-5L (25, 26). However, a new valuation study is on-going (27) and we will use the new UK valuation tariff when this is available, providing the results are valid and robust. QALYs will be generated using an area under the curve approach between adjacent EQ-5D-5L completions (or death). These will be based on the EORTC-8D in a supplementary analysis.

Costs will be based on patient-completed resource use questionnaires (for primary, community and social care) and NHS digital data (for secondary care). The questionnaires will be completed at baseline and every subsequent follow-up. Therapy use will be captured in the CRFs. Unit costs will be taken from resources such as NHS reference costs, Personal Social Services Research Unit (PSSRU) report, electronic market information tool (eMIT) and British National Formulary (BNF). We will use the prevailing drug list prices at the time of analysis.

In the trial analysis, regression models will be used to adjust for baseline imbalance and account for cost-QALY correlations. Where appropriate, we will mirror the statistical team approach to incorporating control variables and adjust for the specified stratification factors (excluding centre). We will assess the type and degree of missing data and evaluate whether the assumption of missing at random (MAR) holds (28). If that is the case, multiple imputation will be used to impute missing data. Should MAR not hold we will explore the impact of alternative assumptions (29). We will report incremental cost-effectiveness ratios (ICERs) (30) at trial end however the primary end-point will be based on lifetime expected costs and outcomes generated from a decision analytic model.

A decision-analytic model being developed in FLAIR will allow the extrapolation of costs and consequences of the treatment strategies over a lifetime horizon. The FLAIR decision model is a Markov model with health states based around CLL response criteria. The final model will be agreed with patient and clinician collaboration. Parameter values will be derived from the proposed trial and other relevant datasets (such as FLAIR and ARCTIC (ISRCTN16544962)) and reviews of the literature. Survival will be extrapolated using parametric survival curves selected using guidance from the NICE Decision Support Unit (31). Incremental cost effectiveness ratios (ICERs) will be generated over a lifetime horizon in reference to the £20,000-£30,000 per QALY willingness to pay threshold. We will conduct extensive deterministic sensitivity analyses and capture total parameter uncertainty using a

probabilistic sensitivity analyses. Results will be represented as cost-effectiveness acceptability curves (32) and net monetary benefit distributions.

As part of the interim analysis, we will use the decision model to explore the cost-effectiveness of treatment breaks and generate value of information estimates to inform study continuation decisions (33). Costs and benefits post 12 months will be discounted at a rate of 3.5% per annum as per NICE guidance. NICE is currently updating the guidance for technology appraisals and we will review the planned methods stated here taking into consideration the updated guidance when published.

A full health economics analysis plan (HEAP) will be written before any analysis is undertaken.

#### **19.4.4 Quality of life (EQ-5D-5L, QLQ-C30, QLQ-CLL)**

Mean Quality of Life (QoL) scores and 95% CIs adjusted for the baseline score will be calculated for all domains of the EORTC QLQ-C30 and CLL specific module, EORTC QLQ-CLL, for each treatment group at each assessment time-point and overall. Additionally, a mixed-model based analysis will be carried out accounting for the baseline QoL, stratification factors, time, patient, and treatment strategy. The aim of this analysis is to show the superiority of the intermittent treatment strategy, in line with the hypothesis of reduced side effects and increased QoL.

#### **19.4.5 Summative Treatment-free Interval**

This is defined as the time to treatment strategy failure, excluding any time spent on treatment. This is equivalent to the total time spent on trial minus the total time spent on treatment. Alternatively the sum of all treatment-free intervals. In addition, the median summative time on treatment annually post randomisation will be estimated using the Kaplan-Meier method. By design this endpoint should confirm compliance with the intermittent strategy by showing superiority in the intermittent strategy when compared to the continuous strategy with respect to more time spent off treatment.

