### **Randomisation Pathway: overview of pausing / resuming and continuous treatment strategies**

To be eligible for randomisation, previously treated participants will have been treated with continuous ibrutinib for at least 3 years and must have been in clinical remission for at least the last 12 months; whereas front-line participants from FLAIR will have been treated for 6 years with ibrutinib in FLAIR and be in clinical remission for at least the last 12 months. Participants will be randomised 1:1 to either intermittent ibrutinib, known as the 'pausing ibrutinib' arm, or continuous ibrutinib treatment.

*'Continuous ibrutinib' arm*

Participants randomised to continuous treatment will receive ibrutinib (oral) 420mg per day (or other reduced dose, if that dose has been stable for the past 6 months and there are no unresolved toxicities) until strategy failure, defined as active disease as per 2018 iwCLL criteria, death, or the end of the trial.

*'Pausing ibrutinib' arm*

Participants randomised to the 'pausing ibrutinib' arm (intermittent treatment strategy) will pause ibrutinib treatment immediately following randomisation, and restart when the restart criteria are met. When treatment restarts, participants restart ibrutinib treatment at the standard dose (or their previous stable reduced dose) until the treatment pausing criteria are met. The pausing and resuming criteria are assessed locally every 3 months at standard clinic visits. Participants can pause and restart treatment multiple times until treatment strategy failure (defined as active disease per 2018 iwCLL criteria) whilst on treatment, death, or end of the study.

In order to begin the initial ibrutinib pause in the pausing ibrutinib arm, all criteria below must be met and maintained continuously for preceding 12 months:

- No palpable lymph nodes and
- No palpable spleen, and
- ALC  $<5 \times 10^9/L$

Criteria to resume/ restart ibrutinib in 'pausing ibrutinib' arm:

Any one of:

[figure not shown]
- Palpable lymph nodes ( $\geq 2\text{cm}$ ), or
- palpable spleen, or
- ALC  $\geq 5 \times 10^9/L$ .

Criteria for subsequent ibrutinib pause(s) (second and subsequent pausing treatment breaks):

- Received at least a further 12 months of ibrutinib, and
- No palpable lymph nodes, and
- No palpable spleen, and
- $<5 \times 10^9/L$  ALC for at least 6 months.

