Participants randomised to the intermittent treatment arm will pause ibrutinib treatment immediately following randomisation, and restart when the restart criteria are met (see Section 13.8.3; the restart criteria do not indicate active disease as per 2018 iwCLL criteria). When the re-start criteria are met participants will receive ibrutinib (oral) 420mg per day (or other reduced dose, if that dose has been stable for the past 6 months and there are no unresolved toxicities) until treatment failure (active disease per 2018 iwCLL criteria) whilst on treatment or death. If these participants demonstrate active disease whilst on the planned treatment pause they will initially resume ibrutinib and the criteria for treatment failure would be met if they present with active disease at the next follow up (in which case the time to treatment failure would be backdated to when active disease was first demonstrated). Those randomised to the continuous treatment arm will receive ibrutinib (oral) 420mg per day (or other reduced dose, if that dose has been stable for the past 6 months and there are no unresolved toxicities) until treatment failure (active disease) as per 2018 iwCLL criteria or death.

The Clinical Need pathway is a prospective, national, multicentre, open-label, single-arm, non-randomised cohort to assess the safety and overall survival of patients receiving continuous ibrutinib treatment. Participants exiting the FLAIR trial who are not eligible for randomised study because they have signs of progressive or returning CLL after completing 6 years of ibrutinib treatment within FLAIR, but prior to entry into STATIC, can join the Clinical Need Cohort. Participants in the Clinical Need Cohort

will receive treatment during the trials 6 year recruitment period and for the 3 years of follow up, meaning that participants will be on the trial for between 3-9 years, depending upon when they enter the trial. Up to 30 patients are expected to enter into the Clinical Need Cohort. Patients will continue receiving continuous ibrutinib, either at the standard dose, or a stable reduced dose.

Front-line participants entering either the Randomisation pathway or the Clinical Need cohort from the FLAIR trial should enter STATIC on completion of treatment in FLAIR, with no break in therapy, with the exception of participants who have completed the 6 years of treatment in FLAIR prior to STATIC opening.

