### 13.8 Randomisation Pathway: Assessments while on study

Participants randomised to the continuous treatment pathway will receive ibrutinib (oral) 420mg per day (or other reduced dose, if that dose has been stable for the past 6 months and there are no unresolved toxicities other stable reduced dose) until active disease leads to the requirement to change to an alternative therapy in the opinion of the local Investigator (strategy failure) or death.

Participants randomised to the intermittent treatment strategy will pause treatment immediately following randomisation, and restart when the restart criteria are met. When treatment restarts, participants restart treatment with ibrutinib at the standard dose (or other reduced dose, if that dose has been stable for the past 6 months and there are no unresolved toxicities) until the treatment stop criteria are met.

The pausing and resuming criteria will be assessed locally every 3 months, at standard clinic visits. Participants can pause and restart treatment multiple times until active disease whilst on treatment leads to the requirement to change to an alternative therapy, death, or the end of the trial. Participants who demonstrate active disease whilst on the treatment pause will initially resume ibrutinib treatment, and the criteria for treatment failure will only be met if active disease is present at the subsequent follow up.

Refer to Section 13.8.3 for pausing and re-starting criteria.

Participants randomised to either pathway will be assessed as per standard of care clinic visits every 3 months, and data collected for the trial 6 monthly.

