#### **17.4.6 Summative treatment-free Interval**

This is defined as the time to treatment strategy failure, excluding any time spent on treatment. This is equivalent to the total time spent on trial minus the total time spent on treatment. Alternatively the sum of all treatment-free intervals. For example, for a participant on the intermittent strategy, this is their time on trial minus any time spent on treatment due to hitting the restart criteria, whereas for a patient in the continuous strategy, this is the time spent off treatment (for example, due to toxicity breaks) whilst on trial. If a participant does not experience treatment failure or death during the trial they will be considered censored at the time of analysis.

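### Longer treatment-free time in the pausing arm cannot confirm compliance with the intermittent strategy, because that result is near certain even when most of the arm does not pause

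*Protocol*

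**What the plan says.** Protocol section 19.4.5 gives the endpoint a purpose: "By design this endpoint should confirm compliance with the intermittent strategy by showing superiority in the intermittent strategy when compared to the continuous strategy", measured by more time off treatment. The same section defines the quantity: "This is equivalent to the total time spent on trial minus the total time spent on treatment". Section 17.4.6 adds that "for a patient in the continuous strategy, this is the time spent off treatment (for example, due to toxicity breaks) whilst on trial", and on censoring: "If a participant does not experience treatment failure or death during the trial they will be considered censored at the time of analysis".

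In the experimental arm time off drug is built into the design. Section 8.1 states: "Participants randomised to the intermittent treatment arm will pause ibrutinib treatment immediately following randomisation, and restart when the restart criteria are met". Section 13.8 adds: "The pausing and resuming criteria will be assessed locally every 3 months, at standard clinic visits". The same section says that trial data are collected every 6 months.

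Section 19.4 sets the default level for secondary endpoints, "All analyses will be conducted with a 2.5% significance level unless stated otherwise", and the default population, ITT. Section 19.4.5 also plans a Kaplan-Meier estimate of median summative time on treatment by year, without saying whether it is shown by arm.

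**The concern.** The sentence moves from a comparison between arms to a conclusion about behaviour within one arm. Compliance with the intermittent strategy means pausing at randomisation, restarting when a section 13.8.3 criterion is met, not restarting without one, and pausing again when eligible. The comparison measures none of these. It asks only whether one arm, told to stop, spent more time off drug than another arm, told to continue. The null hypothesis is false by construction for any appreciable uptake.

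The measure can also move the wrong way. A participant who meets a restart criterion and stays off drug departs from the strategy, yet adds treatment-free time and strengthens the result that is supposed to show compliance.

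This matters more in a non-inferiority trial than in a superiority trial. Pausing-arm participants who never pause make the arms alike and pull the ITT hazard ratio towards 1. A compliance check that passes anyway would give false reassurance about that ITT result.

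**Working it through.** **1. The plan's own figure.** No figure is given for the treatment-free-interval test, so the reference point is the primary sample size in section 18.1: margin 1.33, one-sided 2.5%, 80% power, 379 events. Schoenfeld with 1:1 allocation: 4 × (1.960 + 0.842)² / (ln margin)². A margin of 4/3 gives 379.35, matching 379. A margin of 1.33 gives 387 after rounding up, within 3%. The 5.84-year overall median also reproduces (5.842 years from a 45%/55% mix of medians 10 and 4 years).

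**2. Inputs for the superiority test.**
- From the protocol: 800 randomised 1:1, so 400 per arm (sections 3 and 18.1); 3 to 9 years on trial (8.1); the 4- and 10-year failure mix (18.1); 2.5% level (19.4), taken as one-sided.
- Assumed, because the protocol gives no figure: 30% of the continuous arm, and of pausing-arm participants who never pause, have one toxicity break of mean 2 months. Those who pause alternate between breaks of median 6, 12, 33 or 56 months and 12 months on drug. The 33 and 56 months are the off-drug remission medians quoted in section 6.3.
- The protocol names no test, so three were tried: Wilcoxon, Welch, and log-rank on the treatment-free-time scale.

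**3. Simulation results: chance that superiority is shown.**

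| Share of pausing arm that pauses at all | Wilcoxon and log-rank | Welch |
|---|---|---|
| 100%, 50%, 25% | 1.00 | 1.00 |
| 15% | 0.98–1.00 | 1.00 |
| 10% | 0.77–0.89 | 1.00 |
| 5% | 0.25–0.48 | 1.00 |

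Ranges are over the four break lengths. A separate simulation with breaks of 6 to 33 months gave 97 to 99% at 15%.

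**4. Hand check of the Wilcoxon column.** Suppose a share c pauses and every pauser has more time off than every continuous participant. Then P(pausing > continuous) + ½P(tie) = 0.5 + 0.5c. About 70% of everyone else has zero time off, so the tied share is 0.7 × (2 − c)/2 and the tie correction is 1 − (tied share)³. The expected statistic is z = 0.5c × √(12 × 400 × 400/801) / √(tie correction), with √(12 × 400 × 400/801) = 48.96.
- c = 0.25: tied share 0.6125, correction 0.770, z = 6.12/0.878 = 6.97, power Φ(6.97 − 1.96) = 1.00.
- c = 0.15: tied share 0.6475, correction 0.729, z = 3.67/0.854 = 4.30, power Φ(2.34) = 0.99.
- c = 0.10: tied share 0.665, correction 0.706, z = 2.45/0.840 = 2.91, power Φ(0.95) = 0.83.

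These agree with the simulation.

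**5. Response to restart violations** (everyone pauses, 12-month median break):

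| Break length relative to plan | Mean years off drug, pausing arm | Continuous arm | Power (Wilcoxon, Welch) |
|---|---|---|---|
| 0.5× (early restart) | 1.86 | 0.05 | 1.00 |
| 1× | 2.58 | 0.05 | 1.00 |
| 1.5× | 2.96 | 0.05 | 1.00 |
| 2× | 3.20 | 0.05 | 1.00 |
| 3× (late restart) | 3.48 | 0.05 | 1.00 |

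The test result is the same throughout. The quantity itself grows with late restart.

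**6. What the check could miss in the ITT analysis.** Suppose the hazard ratio under full compliance equals the 1.33 margin and non-pausers have the control hazard, so the ITT hazard ratio is roughly 1.33^c. With 379 events and the 2.35% final level, P(non-inferiority in ITT) = Φ(√(379/4) × ln(1.33/HR) − 1.986).
- c = 1: 2.35%.
- c = 0.75: HR 1.238, Φ(9.734 × 0.0713 − 1.986) = 9.8%.
- c = 0.50: HR 1.153, Φ(9.734 × 0.1426 − 1.986) = 27.5%.

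At each of these levels the treatment-free-time test is certain to succeed. These figures are for ITT alone, not for the trial's decision rule.

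**The case against.** The strongest reply has four parts.

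**Nothing formal hangs on the sentence.** It can be read as the expected direction of a secondary endpoint. It names no test or threshold and gates neither PP membership nor the primary conclusion. That limits the consequence. But the text does say that superiority should confirm compliance, and no choice of test in a statistical analysis plan would make that valid.

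**An estimate is planned too.** The Kaplan-Meier summary of time on treatment, if shown by arm, would expose gross non-pausing: with most of the arm never pausing, its median would lie near full time on drug. This stands. It would still not show whether restarts followed the criteria.

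**The primary result has its own safeguard.** Section 19.1 removes from the PP population those who did not take up their strategy, as well as major violations judged by the Chief Investigator. Section 19.3 requires non-inferiority in both PP and ITT. A reader might infer from the 27.5% above that the trial could easily declare non-inferiority falsely. The documents do not support that: under the joint rule the false-positive rate cannot exceed the PP rate, about 2.35% at the margin if non-uptake is unrelated to prognosis (an assumption). Nor does anything show that late restart biases towards non-inferiority.

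**Adherence is watched elsewhere.** Diary cards (12.2), 3-monthly review (13.8.1), violation reports (13.16) and annual review of time on breaks by the data monitoring committee (19.2.1) all exist. So the protocol does not lack adherence monitoring. None of these, as described, reports treatment status against the section 13.8.3 criteria, and none alters what section 19.4.5 says superiority shows.

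**Conclusion.** The point holds as a flaw in the stated compliance inference. Superiority in treatment-free time is near certain at about 15% uptake or more, does not react to early restart, and moves favourably with late restart, so it cannot confirm compliance. Only at about 10% uptake or below might the test fail, and that depends on which test is used.

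The size rests on assumed break lengths (6 to 56 months), toxicity-break frequency and all-or-nothing pausing. The conclusion did not change across the break lengths tried.

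The stronger reading, that undetected non-adherence undermines the non-inferiority conclusion itself, is not supported, because of the joint PP and ITT requirement. What remains is false assurance about compliance, chiefly when the ITT result is interpreted.

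**What to change.** In section 19.4.5, delete the statement that superiority confirms compliance. Keep treatment-free time as an outcome estimated by arm, and state that the planned Kaplan-Meier summary of time on treatment is also given by arm.

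Report adherence directly, with 95% confidence intervals, from the treatment and disease-assessment data that the trial records:
- the proportion of the pausing arm who paused at randomisation;
- the proportion restarted after meeting the section 13.8.3 restart criteria, and the delay;
- the proportion of restarts made without those criteria being met;
- the proportion of the continuous arm with unplanned breaks over 28 days.

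State that these figures will be used when interpreting the ITT and PP results. No pause or restart rule changes.

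The cost is one reworded sentence and one derived table. Visits are 3-monthly but data are collected 6-monthly (section 13.8), so the timing of restarts can be resolved only as finely as the recorded dates and that data capture allow. Whether the case report form holds the findings of both visits in each 6-month period cannot be told from the protocol and should be checked before the table is specified.
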